5.2.2. Screening period (up to 7 days before Baseline visit)

All assessments during the study are performed as listed in Table 1.

The screening assessments are initiated after completion of the informed consent process, including provision of signed consent for participation.

SAEs are reported from the time point when the ICF has been signed.

5.2.3. Baseline - Day -1

A patient study diary in paper format will be provided for the study participants where intake of investigational product is to be recorded.

Patients will be instructed who to contact in case of study related emergencies and will be provided with a study specific patient card.

The questionnaires will be distributed to fill in at the site, but if too burdensome, the option to complete at home will be given.

The option to distribute questionnaires to fill in prior to next visit will be given, and the forms will be supplied.

Patients will be informed to pay attention to changes in health during the study, to be able to report adverse events on their next visit.

5.2.4. Start of Treatment - Day 1

Patients will start treatment and register intake of investigational product. Patients will be instructed to keep empty blisters and bottles, and bring together with unused IMP, to the clinic on Day 16 visit.

Adverse event reporting starts from intake of the first dose of investigational product.

5.2.5. Visit - Day 16

Remaining IMP as well as empty blisters and bottles are collected for drug accountability. The patient study diary will be collected and reviewed.

The questionnaires will be distributed to fill in at the site, but if too burdensome, the option to complete at home will be given.

If questionnaires for Baseline visit and/or for Day 16 visit was supplied for finalization at home prior to the visit, these are to be collected and reviewed for quality reasons.

The option to distribute questionnaires to fill in prior to next visit will be given, and the forms will be supplied.

A PK sample will be taken for compliance purposes.

5.2.6. Visit - Day 45

Remaining IMP as well as empty blisters and bottles, and patient diary are collected, if not done at Visit at Day 16.

 Version No:

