Physical function tests: 6-minute walk test, maximal inspiratory pressure, hand grip strength, accelerometer (Active PAL) will be performed at baseline, and at Days 16, 45 and 90. The tests are non-invasive and constitute a minimal or no risk of injury and take approximately 30 minutes to perform. The physical tests that will be used are also used in the regular clinical follow-up of long COVID and for other conditions. Participants may experience fatigue during the test session, but the test procedure will be adapted to reduce this risk. The benefits of performing the measurements will outweigh the inconvenience for patients.

Patient reported outcomes: A battery of questionnaires, PRO's, will be distributed to the participants at each visit. As these can be exhausting to fill in, the possibility to bring them home for finalization will be offered, as well as the option to fill in prior to next visit.

Nasal swabs and venipuncture: Nasal swabs for antigen tests, performed at screening and baseline visits, and venipuncture for routine blood sampling as well as research blood samples will be performed at baseline, day 16, 45 and 90. They are standard procedures in routine health care and constitute no risk to the patient but may cause minor pain and discomfort.

In summary, the potential benefits of nirmatrelvir/ritonavir treatment are considered to outweigh the foreseeable risks.

 Version No:

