4.2. Description of Objectives, Endpoints and Estimands

The primary, secondary and tertiary/exploratory objectives and endpoints assessed (as described in the schedule of activity) to assess the effect of oral Administration of nirmatrelvir/ritonavir in patients with post-COVID-19 symptoms are summarized in the table below.

Objectives	Endpoints	Estimand
Primary	Primary	Primary
To evaluate the effect of oral administration of nirmatrelvir/ritonavir at Day 16 on quality of life	Change from baseline on the EQ-5D-5L VAS scale at day 16	Estimand 1: This estimand is intended to provide a population-level estimate of the mean treatment effect (nirmatrelvir/ritonavir relative to placebo) on a continuous endpoint over time for all randomized/evaluable participants. The difference of Day 16 on EQ-5D-5L VAS scale between the nirmatrelvir/ritonavir and placebo arms in participants with long COVID estimated with a longitudinal analysis that controls for baseline assessment
Secondary	Secondary	Secondary
To evaluate the effect of oral administration of nirmatrelvir/ritonavir in patients with post-COVID-19 symptoms over time on quality of life	Change from baseline on the EQ-5D-5L VAS scale at day 45 and on Day 90	Estimand 1 (see above)

 Version No:

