 2.0 Final

 Date:
 10 March 2023

 EudraCT No:
 2022-003855-32

The questionnaires will be distributed to fill in at the site, but if too burdensome, the option to complete at home will be given.

If questionnaires for any visit up to Day 45 visit was supplied for finalization at home, these are to be collected, and reviewed for quality reasons, if not done earlier.

The option to distribute questionnaires to fill in prior next visit will be given, and the forms will be supplied.

5.2.7. Day 90

Remaining IMP as well as empty blisters and bottles, and patient diary are collected, if not done earlier.

The questionnaires will be distributed to fill in at the site, but if too burdensome, the option to complete at home will be given with instructions on how to send back to the clinic.

All questionnaires for visits up to Day 90 visit supplied for finalization at home are to be collected, if not done earlier, and reviewed for quality reasons.

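### The take-home option covers the primary EQ-5D-5L VAS and sets no explicit completion deadline, so a Baseline form could be finished after the first dose and a Day 16 form after the visit day (minor)

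*Protocol*

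**What the plan says.** Section 4.2 defines the primary endpoint as "Change from baseline on the EQ-5D-5L VAS scale at day 16", to be "estimated with a longitudinal analysis that controls for baseline assessment". Both the Baseline and the Day 16 form therefore enter the primary result. The VAS in the appended EQ-5D-5L asks for the patient's health today.

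Table 1 schedules the EQ-5D-5L at Baseline (Day -1) and at Day 16, each with a ±0-day window, and section 5.2.2 makes Table 1 govern all assessments.

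Section 5.2.3 then states: "The questionnaires will be distributed to fill in at the site, but if too burdensome, the option to complete at home will be given". The same offer recurs in 5.2.5 to 5.2.7. Section 3 says of the questionnaires in general that "the possibility to bring them home for finalization will be offered". In Table 1 the EQ-5D-5L carries the same PRO marker (j) as the other questionnaires, and the footnote gives an option of home completion before the next visit. No passage exempts the EQ-5D-5L.

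On return of forms:
- Section 5.2.5 (Day 16): if "questionnaires for Baseline visit and/or for Day 16 visit was supplied for finalization at home prior to the visit, these are to be collected".
- Section 5.2.6 (Day 45): "If questionnaires for any visit up to Day 45 visit was supplied for finalization at home, these are to be collected".
- Section 5.2.7 (Day 90): "All questionnaires for visits up to Day 90 visit supplied for finalization at home are to be collected, if not done earlier".

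On Day 1, section 5.2.4 says: "Patients will start treatment and register intake of investigational product".

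**The concern.** A VAS score belongs to the day on which it is marked. If a Baseline form is finished after dosing has begun, the score may already include some response to treatment, and subtracting or adjusting for it removes part of the effect that the trial is trying to measure. If a Day 16 form is finished late, it describes a time further into the off-treatment period but would be analysed as Day 16; the direction of that error is unknown.

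The exposed variable is the sole primary endpoint, at both of its time points. A statistical analysis plan can classify a late form, but it cannot recover a pre-dose score that was never recorded.

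**Working it through.** **Text check: how long may a form taken home stay out?**

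1. Section 5.1 allows at most five visits, and the visit-time table in 5.2.8 lists Screening, Baseline, Day 16, Day 45 and Day 90. Day 1 is not among them, so the next visit after Baseline is Day 16.
2. The first box in the patient diary is the morning of Day 1. A form taken home on Day -1 has only the rest of that day before the first scheduled dose.
3. Section 8.3.1 allows forms to be filled in the day before a visit. This limits early completion and sets no limit on completion after a visit.
4. Sections 5.2.5 to 5.2.7 have returned forms reviewed for quality, but they name no check of the completion date.

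The ±0-day windows fix the visit. For a form taken home, no sentence fixes the day of completion.

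**Size (illustration only)**

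The protocol gives neither an SD nor the share of forms taken home. The SD can be back-solved from section 10.5: N = 207, 2:1, 10 points, one-sided 0.05, 90% power. With 2:1 allocation, SE = SD × √(4.5/N), so

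SD = 10 / (1.645 + 1.282) × √(207/4.5) ≈ 23.2.

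The figures below use SD 23.1, which returns 90.2% power at N = 207; using 23.18 instead changes them by less than 0.3 percentage points.

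Let f be the share of Baseline forms completed on treatment, g the share of the effect present by then, and b the weight that the analysis gives to baseline. Late forms shift the Baseline difference between arms by 10·f·g, so a true 10 points is estimated as 10 × (1 − b·f·g). All three are assumptions: g = 0.5 and b = 0.5 to 1. A form finished on the evening of Day -1 has g = 0.

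| f | b = 0.5 | b = 1 |
|---|---|---|
| 5% | 9.875 | 9.75 |
| 10% | 9.75 | 9.5 |
| 20% | 9.5 | 9.0 |
| 40% | 9.0 | 8.0 |

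Power = Φ(effect/SE − 1.645). Example with 300 evaluable: SE = 23.1 × √(4.5/300) = 2.83, and 9.5/2.83 − 1.645 = 1.71, which gives 95.7%.

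| Estimated effect | 207 evaluable | 300 | 400 |
|---|---|---|---|
| 10.0 | 90.2% | 97.1% | 99.3% |
| 9.75 | 88.8% | 96.4% | 99.0% |
| 9.5 | 87.4% | 95.7% | 98.7% |
| 9.0 | 84.1% | 93.8% | 97.9% |
| 8.0 | 75.9% | 88.2% | 94.7% |

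The 207 column reflects 48% dropout over the whole study. For a Day 16 endpoint, 300 to 400 evaluable is probably closer. If the whole effect were already present (g = 1), the row for twice the f applies.

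**The case against.** The strongest reply is that the timing is already fixed. Table 1 places the form on Day -1 and Day 16 with no tolerance, Table 1 governs, and the default is completion at the site. The home option changes the place and does not expressly change the day. This stands to the extent that a reader who infers that nothing at all requires timely completion goes too far. It does not close the gap, because the home option reaches the EQ-5D-5L through Table 1's own footnote and gives no deadline for a form that leaves the site.

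Second, collection is not completion. Day 16 is simply the first scheduled visit at which a paper Baseline form can be handed back, even one finished on the evening of Day -1. That is correct. A reader might infer that the protocol plans for Baseline scores to be given after treatment; it does not. It leaves that possible.

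Third, the footnote can be read as inviting patients to fill in the next visit's forms ahead of time. That reading is open, but the offer in 5.2.3 and the collection rule in 5.2.5 do not depend on the footnote.

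Fourth, nothing shows that the short EQ-5D-5L would be the form taken home. Table 1 marks ten questionnaires at Baseline and seven at Day 16. Both counts include the MoCA, which staff administer, leaving nine and six; the MAPS, at Baseline only, is for POTS patients. Heavier Baseline paperwork makes use of the home option plausible there, but says nothing about which form is left over.

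Finally, fallback and out-of-window rules commonly sit in the SAP, and date capture may sit in the eCRF; neither is at hand. That is fair for handling a late form. The instruction to obtain the score before the first dose concerns how the primary measure is collected, and the protocol text is what leaves it open.

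**Conclusion.** The point holds as a minor one. For forms taken home, the protocol sets no explicit deadline relative to the first dose or the visit day, and it does not exempt the primary VAS.

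The expected consequence is small dilution plus noise. A false-positive bias might be inferred, but the documents do not support it: allocation is randomised and blinded, and a Baseline score that has absorbed part of the effect shrinks the difference. Under the assumptions above, losing a full point needs 20% of Baseline forms completed on treatment if b = 1, or 40% if b = 0.5. At 10%, the power loss is 0.7 to 1.4 percentage points with 300 evaluable and 0.3 to 0.6 with 400. These figures rest wholly on the assumed f, g and b and on a back-solved SD; the true size is unknown and probably small. The case for acting is that the remedy costs almost nothing.

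**What to change.** Exempt the EQ-5D-5L from the take-home option at Baseline and Day 16. Require it on site or by same-day dated electronic entry: at Baseline before the first dose, and at Day 16 on the visit day or the day before, as 8.3.1 allows. Record the completion date. Align section 3, sections 5.2.3 to 5.2.7, the PRO footnote to Table 1 and section 8.3.1. Keep the home option for the other self-completed questionnaires.

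Handling of a Baseline form dated after the first dose can be left to the SAP. One option is the screening VAS (Day -7 to Day -2) as fallback, by the same rule in both arms. Eligibility requires a VAS below 50, so that is a selected value and would add some noise equally to both arms.

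The cost is a few sentences and one date field, slightly less flexibility for burdened patients, and possibly a few missing values. If 5% of Day 16 values became missing, power would go from 97.1% to 96.4% with 300 evaluable (SE with N = 285) or from 99.3% to 99.0% with 400 (N = 380). That is about the same as the dilution at f = 10% and b = 0.5, so the gain comes from completing the form on time, not from discarding late ones.

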 2.0 Final

 Date:
 10 March 2023

 EudraCT No:
 2022-003855-32

The questionnaires will be distributed to fill in at the site, but if too burdensome, the option to complete at home will be given.

If questionnaires for any visit up to Day 45 visit was supplied for finalization at home, these are to be collected, and reviewed for quality reasons, if not done earlier.

The option to distribute questionnaires to fill in prior next visit will be given, and the forms will be supplied.

5.2.7. Day 90

Remaining IMP as well as empty blisters and bottles, and patient diary are collected, if not done earlier.

The questionnaires will be distributed to fill in at the site, but if too burdensome, the option to complete at home will be given with instructions on how to send back to the clinic.

All questionnaires for visits up to Day 90 visit supplied for finalization at home are to be collected, if not done earlier, and reviewed for quality reasons.

5.2.8. Early Termination

In case of Early Termination of treatment, the assessments should be completed as soon as possible after decision of treatment withdrawal. When possible, all study assessments should continue in accordance with the Schedule of Assessments until completion of the Day 90 visit.

The estimated time needed for each visit is shown in the table below.

Screening	Baseline	Day 16	Day 45	Day 90
60 minutes 1,5 hours	90 minutes 2,5 hours	60 minutes 2 hours	60 minutes 2,5 hours	40 minutes 1,5 hours

5.3. Biological sampling procedures

5.3.1. Handling, storage, and destruction of biological samples

Blood samples and urine (only for pregnancy test) for safety monitoring will be taken and analyzed according to local procedures. These samples will be destroyed after analysis.

Blood samples for exploratory biomarkers will be collected on Day 1, Day 16 and Day 45. These will be handled and analyzed according to predefined and agreed procedures. The samples will be kept in the biobank for a maximum of 10 years after study completion.

Saliva will be collected for antigen testing of active SARS CoV-2 infection. The sample will be taken and analyzed according to local procedures after which it will be discarded.

Nasopharynx/nasal swab will be collected to confirm SARS CoV-2 infection given positive antigen test. The sample will be taken and analyzed according to local procedures after which it will be discarded.

 Version No:
 2.0 Final

 Date:
 10 March 2023

 EudraCT No:
 2022-003855-32

Detailed sampling and handling procedures are described in a separate document.

5.3.2. Retained research sample for future biomarkers

Retained research samples may be used for research related to the study intervention and COVID-19. Genes and other analytes (e.g., drug metabolites, pharmacokinetics, proteins, RNA, nondrug metabolites) may be studied using the retained samples. Any future analysis will be conducted in accordance with the ICD and EPN approval.

5.3.3. Total volume of blood per subject

The total volume of blood taken from each subject during the study is maximum 200 ml, divided into 34 mL at each draw for safety samples, 4 mL for genetic sample, and 10 mL at each draw for exploratory analyses and the retained research sample.

5.3.4. Biobank

Samples taken in this study are registered in a biobank, Stockholms Medicinska Biobank, and handled according to the current biobank laws and regulations. The samples are coded/pseudonymized to protect the subject's identification. All samples and the identification/code list are stored securely and separately to prevent unauthorized persons from having access to them.

5.4. End of Study

The study ends when the last subject has completed the last follow-up visit. The study may be prematurely terminated as per decision taken at the interim analysis, or by recommendation from the safety monitoring committee, or if recruitment of subjects cannot be met within reasonable time limits. If the study is prematurely terminated or suspended, the investigator should immediately inform the subjects about this and ensure appropriate treatment and follow-up. The regulatory authority should be informed as soon as possible, but no later than within 15 days.

Decision on premature termination is taken by the sponsor.

6. Subject selection

6.1. Study participants

Study participants in the PROLIFIC study will be identified from patients admitted to the Karolinska post-COVID clinic or who participate in Karolinska post-COVID research but may also be reached through advertisement in local media as needed.

6.2. Inclusion criteria

To be included in the study, subjects must meet the following criteria:

- 1. The subject has given written consent to participate in the study.
- 2. ≥18 years of age at the time of the Screening Visit
- 3. Post-acute COVID-19 syndrome (PACS) according to the WHO definition
- 4. EQ-5D-5L VAS< 50

 Version No:
 2.0 Final

 Date:
 10 March 2023

 EudraCT No:
 2022-003855-32

5. All fertile participants must agree to use a highly effective method of contraception for the duration of the study and 28 days after last intake of IMP.

6.3. Exclusion criteria

General exclusion criteria

- 1. Other non-related conditions with PACS like symptoms
- 2. Renal function eGFR eGFRCysC < 60 mL/min/1.73 m²
- 3. Not able to comply with the study protocol
- 4. Previous Paxlovid® treatment
- 5. Pregnancy or breastfeeding
- 6. Drug-drug interaction with ongoing treatment, including concomitant use of *any* medications or substances that are strong inducers of CYP3A4 within 28 days prior to first dose of nirmatrelvir/ritonavir and during study treatment
- 7. Participants who are planning or considering vaccination (including boosters) through Study Day 45
- 8. Active COVID-19 infection as verified by SARS CoV-2 positive antigen test
- 9. Self-reported medical conditions, including:
 - a) Type 1 or Type 2 diabetes mellitus
 - b) Chronic kidney disease
 - Neurodevelopmental disorders (e.g., cerebral palsy, Down's syndrome)
 or other conditions that confer medical complexity (e.g., genetic or
 metabolic syndromes and severe congenital anomalies)
 - d) Active cancer other than localized skin cancer, including those requiring treatment (including palliative treatment), as long as the treatment is not among the prohibited medications that must be administered/continued during the trial period.
 - e) Immunosuppressive disease (e.g., bone marrow or organ transplantation or primary immune deficiencies) OR prolonged use of immuneweakening medications:
 - i. Has received corticosteroids equivalent to prednisone ≥20 mg daily for at least 14 consecutive days within 30 days prior to study entry.
 - ii. Has received treatment with biologics (e.g., infliximab, ustekinumab, etc.), immunomodulators (e.g., methotrexate, 6MP, azathioprine, etc.), or cancer chemotherapy within 90 days prior to study entry';
 - iii. HIV infection with CD4+ cell count <200/mm³.
- 10. History of hospitalization for the medical treatment of acute COVID-19
- 11. Current need for hospitalization or anticipated need for hospitalization within 48 hours after randomization in the clinical opinion of the site investigator.
- 12. Prior/Concomitant Therapy:
 - a) Current or expected use of any medications or substances that are highly dependent on CYP3A4 for clearance, and for which elevated plasma concentrations may be associated with serious and/or life-threatening events during treatment and for 4 days after the last dose of nirmatrelvir/ritonavir. List of potential interactions provided by Pfizer provided in Appendix A.
 - b) Has received or is expected to receive monoclonal antibody treatment, antiviral treatment (e.g., molnupiravir), or convalescent COVID-19 plasma.

 Version No:
 2.0 Final

 Date:
 10 March 2023

 EudraCT No:
 2022-003855-32

Prior/Concurrent Clinical Study Experience:

- 13. Is unwilling to abstain from participating in another interventional clinical study with an investigational compound or device, including those for post-COVID-19 therapeutics, through the long-term follow-up visit.
- 14. Previous administration with any investigational drug or vaccine within 30 days (or as determined by the local requirement) or 5 half-lives preceding the first dose of study intervention used in this study (whichever is longer).
- 15. Known prior participation in this trial or other trial involving nirmatrelvir.

Diagnostic Assessments:

- 16. Known history of any of the following abnormalities in clinical laboratory tests (within past 6 months of the screening visit):
 - AST or ALT level ≥2.5 X ULN
 - Total bilirubin ≥2 X ULN (≥3 X ULN for Gilbert's syndrome)

6.4. Screening

Subject eligibility (that subjects fulfill all inclusion criteria and do not meet any exclusion criteria) is established at the screening visit before randomization.

6.5. Withdrawal criteria

Subjects can discontinue their participation in the study at any time without any consequence to his/her continued treatment. The investigator/sponsor can at any time terminate the study for a subject due to, e.g., unacceptable adverse events/adverse reactions or because the subject does not follow procedures in the study protocol. If the subject discontinues the study, follow-up of this subject will be performed according to the clinic's routine.

7. Study treatments

7.1. Investigational products

Treatment	Investigational product	Dosage form	Route	Strength	Dose regimen	Total Daily dose
Α	Nirmatrelvir	Tablet	Oral	300 mg	Twice daily	600 mg
Α	Ritonavir	Tablet	Oral	100 mg	Twice daily	200 mg
В	Placebo	Tablet	Oral	NA	Twice daily	NA
В	Ritonavir	Tablet	Oral	100 mg	Twice daily	200 mg

 Version No:
